## **Study Protocol and Statistical Analysis Plan with Results**

A total of 69 patients with uncontrolled open-angle glaucoma were recruited at the George Washington University by two glaucoma attending professors. Research protocol approval was obtained from the institutional review board of George Washington University (Washington, DC, USA) under IRB #041, 310 and registered on ClinicalTrials.gov with identifier NCT01956942. Written informed consent was received from all patients, and the protocol followed the Declaration of Helsinki.

This study included all laser trabeculoplasty candidates with open-angle glaucoma on maximally tolerated medical therapy with the need for additional IOP lowering. Patients with end-stage, neovascular, uveitic, or angle closure glaucoma were excluded. In all, 38 patients were randomized to MLT and 31 patients to SLT via a random number generator protocol approved for up to 100 patients. All patients had only one eye included in the study. Patients were allocated to each group without any stratification based on prior characteristics via sealed numbers in a set sequence. Recruitment was concluded after a power analysis revealed an 80% power at a 0.05  $\alpha$  level detecting an average 2.99 mmHg or 16.19% decrease from baseline between the SLT and MLT groups. This level was determined based on prior studies defining a \$3 mmHg or \$20.0% decrease in IOP as a significant difference from baseline.11 Patients, physicians, and researchers were not blinded to the different laser treatments. Each of the two physicians performed both the laser treatments and all subsequent follow-ups for a particular patient.

The MLT group underwent 360° treatment with the IQ 577 nm™ yellow laser (Iridex Corporation, Mountain View, CA, USA) with laser applied to the pigmented trabecular meshwork in a confluent manner. The laser settings for MLT were 1,000 mW, 300 ms duration, 300 µm spot size, and a 15% duty cycle. The SLT group received 360° treatment with the 532 nm Q-switched, frequencydoubled Nd:YAG Selecta II™ (Lumenis Inc, San Jose, CA, USA). The energy for SLT was titrated, between ~0.6 and ~2.0 mJ, based on trabecular meshwork pigmentation to achieve a noticeable gas bubble response, utilizing a 400 µm spot size and a 3 ns duration.

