All patients were treated with one drop of apraclonidine prior to the treatment. Patients were discharged with topical diclofenac 0.1% to use as needed for discomfort. At week 1, patients completed a standardized survey querying discomfort experienced both during and after the procedure and use of the topical diclofenac.

Patients' IOP was measured at predefined intervals of 1 hour and 1-, 6-, 6–12-, 12–24-, 24–36-, and 36–52-week intervals based on a fixed follow-up of 1 and 6 weeks and a tendency to follow these patients every 3–4 months thereafter. Pretreatment IOP values were calculated as the average of up to three preceding visits to reduce fluctuations. Only the preceding visits without the addition of a drop or a laser were included to avoid confounding influences. If patients were examined multiple times within an interval, IOP values were averaged for statistical analysis. Patients' responses were excluded from the analysis if they underwent any interventions that may affect their IOP, including the addition of a topical antihypertensive drop, cataract surgery, cyclophotocoagulation, incisional glaucoma surgery, or further laser trabeculoplasty. However, their data were still included for the intervals up to the time of these interventions. Comparison between groups was calculated with Student's *t*-test for continuous data and a two-tailed Fisher's exact test for categorical data.

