Prior authors defined a successful laser trabeculoplasty as \$3 mmHg IOP decrease or \$20.0% IOP decrease from baseline.6,8 Using these criteria, 29.6% of the MLT and 36.0% of the SLT patients experienced a 20.0% IOP decrease from baseline during the 24–52-week interval (P=0.77). Similarly, 37.0% of the MLT patients and 36.0% of the SLT patients experienced a \$3 mmHg IOP reduction from baseline at the 24–52-week interval (P=1.0).

Patients in each group were also assessed to determine the proportion that required further intervention for their glaucoma during the 52-week follow-up period, indicating a failure of the laser therapy. In the MLT group, a total of 23.7% of patients failed and required further treatment for their glaucoma. A topical antiglaucoma agent was added in 15.8% of the MLT patients, incisional glaucoma surgery was performed in 2.6% of the MLT patients, and transscleral cyclophotocoagulation was performed in 5.3% of the MLT patients. In the SLT group, 12.9% of the patients failed, with all the failures due to the addition of another topical antiglaucoma medication. Although there were a greater number of failures in the MLT group (23.7%) compared to the SLT group (12.9%), the analysis did not meet significance in each individual category or when considered in sum (P=0.22). No patient in either group experienced any complications, other than a transient rise in IOP.

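### The 52-week failure rates divide by all randomised patients, although at least 2 per arm have neither a recorded failure nor a usable reading after week 24

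*Combined protocol and SAP*

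**What the plan says.** The methods text states that "38 patients were randomized to MLT and 31 patients to SLT". After the visits at 1 and 6 weeks, follow-up rests on "a tendency to follow these patients every 3–4 months thereafter". IOP data are dropped once a patient has an intervention that may affect IOP. The listed interventions include cataract surgery, but data from intervals before the intervention are kept.

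The Results define failure through "the proportion that required further intervention for their glaucoma during the 52-week follow-up period, indicating a failure of the laser therapy". They then state: "In the MLT group, a total of 23.7% of patients failed and required further treatment for their glaucoma", and for the other arm "In the SLT group, 12.9% of the patients failed". The MLT total is broken down by type of intervention, beginning with "A topical antiglaucoma agent was added in 15.8% of the MLT patients". The P value given for total failures is 0.22.

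The paragraph before it gives success rates for the 24–52-week window: "29.6% of the MLT and 36.0% of the SLT patients experienced a 20.0% IOP decrease from baseline" (P=0.77). For the 3 mmHg criterion, "37.0% of the MLT patients and 36.0% of the SLT patients experienced" that reduction (P=1.0).

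The Results also report a Kaplan–Meier curve with a log-rank P of 0.31. The text gives no count of patients lost, no length of follow-up for patients without failure, and no rule for how such patients enter the failure proportion.

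**The concern.** A crude proportion over all randomised patients equals the 52-week risk only if every patient counted as a non-failure was observed without failure to week 52. The late success rates rest on clearly fewer patients than were randomised, and visits after week 6 were not fixed, so incomplete follow-up is to be expected. A patient who left at, say, week 10 without failing carries no information about weeks 10 to 52, but the crude rate credits that patient with a full event-free year.

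At stake is how the two failure percentages are read. They are presented as risks over 52 weeks, and failure is the outcome on which MLT looks less favourable. If follow-up was incomplete, each percentage is too low as a 52-week risk, and no confidence interval in the text shows the uncertainty.

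**Working it through.** **Inputs.** Randomised: 38 MLT and 31 SLT (methods text). Failure: 23.7% and 12.9%. Success at 24–52 weeks: 29.6% and 37.0% for MLT, 36.0% on both criteria for SLT (all Results).

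**Step 1: recover the counts.** All fractions with a denominator up to the arm size were checked against each printed percentage.

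| Printed | Arm | Only fraction that fits |
|---|---|---|
| 23.7% | MLT | 9/38 |
| 12.9% | SLT | 4/31 |
| 29.6% | MLT | 8/27 |
| 37.0% | MLT | 10/27 |
| 36.0% | SLT | 9/25 |

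The MLT components agree with the total: 6/38 (15.8%) + 1/38 (2.6%) + 2/38 (5.3%) = 9/38. The late denominators are confirmed by the stated P values. Two-tailed Fisher gives 0.77 for 8/27 vs 9/25 and 1.00 for 10/27 vs 9/25, as printed.

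**Step 2: lower bound on patients with neither a failure nor a late reading.** Patients without a usable 24–52-week reading: 38 − 27 = 11 MLT and 31 − 25 = 6 SLT. At most 9 and 4 of these can be failures. This leaves at least 11 − 9 = 2 MLT and 6 − 4 = 2 SLT. Each failure that still contributed a late reading before the intervention adds one to this number, up to 11 and 6.

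**Step 3: size in each arm.** Let k (0 to 9) be the MLT failures without a late reading, and j (0 to 4) the same for SLT. The patients with neither a failure nor a late reading then number 11 − k and 6 − j. Suppose that all of them left before contributing useful follow-up, and that their risk was that of the patients who stayed. The failure rates become

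- MLT: 9/(38 − (11 − k)) = 9/(27 + k)
- SLT: 4/(31 − (6 − j)) = 4/(25 + j)

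| Case | MLT | SLT |
|---|---|---|
| Stated | 9/38 = 23.7% | 4/31 = 12.9% |
| Minimum of 2 removed per arm (k=9, j=4) | 9/36 = 25.0% | 4/29 = 13.8% |
| Outer bound (k=0, j=0) | 9/27 = 33.3% | 4/25 = 16.0% |

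The Results say that the MLT failures came more in the early period, which points to high k. The MLT outer bound is therefore unlikely.

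**Step 4: the gap between arms.** The stated gap is 23.7 − 12.9 = 10.8 points. Over all 10 × 5 = 50 pairs (k, j), the gap runs from 25.0 − 16.0 = 9.0 (k=9, j=0) to 33.3 − 13.8 = 19.5 (k=0, j=4). Seven pairs fall below the stated gap: (7,0), (8,0), (8,1), (9,0), (9,1), (9,2) and (9,3).

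**Step 5: significance.** Two-tailed Fisher on 9/38 vs 4/31 gives 0.36, not the stated 0.22. Neither one-tailed Fisher (0.20) nor uncorrected chi-square (0.25) gives 0.22. Over the 50 pairs, Fisher P runs from 0.12 (0,4) to 0.53 (9,0). It is 0.35 at the minimum (9,4).

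Counting the minimum 2 per arm as failures gives 11/38 = 28.9% vs 6/31 = 19.4% (P=0.41). Doing so in MLT only gives 28.9% vs 12.9% (P=0.15), and in SLT only 23.7% vs 19.4% (P=0.77).

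**The case against.** **A missing reading is not unknown failure status.** This stands. IOP data were dropped after cataract surgery, which is not among the reported failure types. Such a patient may have been followed to week 52 with failure status known and would then belong in the denominator. The documents do not say, so the understatement is conditional.

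**The time-to-event analysis is already there.** This largely stands. The log-rank test is reported, and Figure 3, which is not visible in the extracted text, may show numbers at risk and censoring. What remains is that the failure paragraph gives crude percentages as 52-week figures with a separate P value.

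**The effect may be small.** At the guaranteed minimum it is: 1.3 points in MLT (25.0 − 23.7) and 0.9 in SLT (13.8 − 12.9).

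**Stronger readings to avoid.** A reader might infer that the bias is larger in MLT, where 11 patients lack a late reading against 6, and that the gap between arms is therefore understated. The documents do not support this. The difference between 11 and 6 may consist entirely of recorded failures (9 vs 4), which are already counted. At the minimum, the affected share is 2/38 = 5.3% in MLT and 2/31 = 6.5% in SLT. The gap can shrink as well as grow.

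A reader might also set this against the statement that the lasers are comparable. That statement concerns IOP decreases, and the Results openly say that MLT had more failures.

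**Conclusion.** The concern holds in a limited form. It is certain that the failure rates use all 38 and 31 randomised patients. It is also certain that at least 2 patients per arm have neither a recorded failure nor a usable reading after week 24 and are counted as event-free to week 52. If any of them left before week 52, that arm's crude rate understates its 52-week risk. The rate becomes 25.0% (MLT) and 13.8% (SLT) if the minimum 2 per arm left early, with outer bounds of 33.3% and 16.0%.

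These figures rest on two assumptions: that patients who left had the same risk as those who stayed, and that the 27 and 25 with a late reading were followed to week 52. The second is generous, because one reading in the window does not show follow-up to its end.

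The direction of the effect on the gap is not established (9.0 to 19.5 points against 10.8). The difference between arms stays non-significant for every pair examined, and also when the minimum 2 per arm are counted as failures. This is a correction to how a risk is reported, not a reversal of a finding.

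**What to change.** In the failure paragraph, replace the crude percentages as 52-week risks with the 52-week Kaplan–Meier cumulative failure and its 95% CI in each arm, from the curve already produced. The raw counts, 9 of 38 and 4 of 31, can stay as counts.

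- State the censoring rule: each patient without failure is censored at the last visit at which failure status was known. A patient with cataract surgery but known later status then stays at risk until that visit.
- Give the numbers at risk at weeks 12, 24, 36 and 52, and the number per arm lost before week 52.
- Use the log-rank test (P=0.31) as the between-arm comparison in place of P=0.22, which does not reproduce from the stated counts with the two-tailed Fisher test named in the methods.

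The work is slight, since the curve and the test exist. The cost is in the message: failure figures that may be slightly less favourable, and wider stated uncertainty.

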## Results

There was no statistically significant difference in demographic characteristics between groups, as seen in Table 1. The MLT patients had a higher average starting IOP (18.26 mmHg) than the SLT group (16.85 mmHg), approaching significance (P=0.08). Both groups had very similar 1 hour posttreatment IOP, 15.15 mmHg in the MLT group and 15.65 mmHg in the SLT group. An IOP spike was defined as an elevation of .5 mmHg from the pretreatment mean. Incidence of post-procedure spikes were 5.3% and 12.9% in the MLT and SLT groups, respectively, but this difference was not statistically significant (P=0.4). No group experienced any anterior chamber inflammation upon examination at the 1 week follow-up time point.

Follow-up data at the 1-, 1–6-, 6–12-, 12–24-, 24–36-, and 36–52-week intervals were tabulated as absolute IOP decreases from pretreatment levels (Figure 1) and percentage IOP decreases from baseline (Figure 2). These data demonstrated that both MLT and SLT provided comparable decreases in IOP from baseline as both an absolute measurement and a percentage decrease at all intervals up 52 weeks (*P*.0.05). In addition, the confidence intervals at each time period were, 3 mmHg when viewed as an absolute decrease in IOP and, 20.0% when viewed as a percentage decrease from baseline IOP, except one outlier interval (week 24–36 in Figure 1). A Kaplan–Meier curve is demonstrated in Figure 3. As expected, the larger proportion of failures in the MLT group produced a lower curve, with more of the MLT failures occurring in the early period. However, the survival curve steps in both groups were similar at later intervals, leading to a log-rank *P*-value of 0.31.

The data from the standardized pain survey (scale of 0= none to 10= severe) revealed that the MLT patients experienced a mean 1.34/10 during treatment and 0.89/10 during the 1 week posttreatment period, while the SLT patients noted 2.83/10 during treatment and 2.81/10 during the 1 week posttreatment period. The MLT patients on average experienced less pain both during and after the treatment (P=0.005).

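### The P value of 0.22 for total failures does not match the specified two-tailed Fisher's exact test, which gives 0.36 on the printed percentages

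*Combined protocol and SAP*

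**What the plan says.** The statistical paragraph that closes the methods (Study Protocol and Statistical Analysis Plan with Results) assigns "a two-tailed Fisher's exact test for categorical data". The randomisation paragraph in the same section gives the arm sizes: "38 patients were randomized to MLT and 31 patients to SLT".

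The last paragraph of the Results defines failure as needing further glaucoma intervention within 52 weeks. It puts MLT failures at 23.7% and splits them into three kinds: "A topical antiglaucoma agent was added in 15.8% of the MLT patients", with incisional surgery in 2.6% and cyclophotocoagulation in 5.3%. For the other arm it says "In the SLT group, 12.9% of the patients failed", all through an added drop. It then concludes that "the analysis did not meet significance in each individual category or when considered in sum (P=0.22"). No other test is named for this comparison.

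A separate time-to-failure analysis appears earlier in the Results, "leading to a log-rank *P*-value of 0.31".

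**The concern.** The percentages, the arm sizes and the test are all printed, so a reader can recompute this P value, and the printed figure does not come back. Either the P value is wrong, or the test or the patients behind it differ from what the document states. Failure is one of the efficacy outcomes on which the two lasers are compared, and 0.22 is the only P value given for its total. Anyone reusing the result would find a figure that its own description does not support. Significance is not at stake, since both values are well above 0.05.

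**Working it through.** **Step 1. Counts.** The inputs are the arm sizes (38 MLT, 31 SLT) from the randomisation paragraph and the failure percentages from the last Results paragraph.

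- MLT total: 9/38 = 23.7%. No other count over any denominator up to 38 rounds to 23.7%.
- SLT total: 4/31 = 12.9%. No other count over any denominator up to 31 rounds to 12.9%.
- MLT by category: 6/38 = 15.8%, 1/38 = 2.6%, 2/38 = 5.3%. Since 6 + 1 + 2 = 9, the breakdown agrees with the total.

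**Step 2. The specified test.** With 13 failures among 69 patients, the number k falling in the MLT arm under the null hypothesis has probability

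Pr(k) = C(38, k) × C(31, 13 − k) / C(69, 13).

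The observed k = 9 has probability 0.1327. The two-tailed P value sums every outcome no more probable than that:

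- upper side, k = 9 to 13: 0.2045
- lower side, k = 0 to 5: 0.1523 (k = 5 has probability 0.1024; k = 6 has 0.1878 and is left out)

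P = 0.2045 + 0.1523 = **0.357**. The printed value is 0.22.

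**Step 3. Do the other categorical P values reproduce under this test?**

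| Comparison | Counts | Two-tailed Fisher P | Printed P |
|---|---|---|---|
| IOP spikes | 2/38 vs 4/31 | 0.397 | 0.4 |
| 20% reduction, weeks 24–52 | 8/27 vs 9/25 | 0.769 | 0.77 |
| 3 mmHg reduction, weeks 24–52 | 10/27 vs 9/25 | 1.0 | 1.0 |
| Total failures | 9/38 vs 4/31 | 0.357 | 0.22 |

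The denominators 27 and 25 are not printed. They are inferred as the only ones within the arm sizes that give 29.6% and 37.0% (27) and 36.0% (25).

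The statement about individual categories also holds: added drop 6/38 vs 4/31, P=1.0; incisional surgery 1/38 vs 0/31, P=1.0; cyclophotocoagulation 2/38 vs 0/31, P=0.50.

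**Step 4. Does another common two-group test, or a slip of one in a count, give 0.22?** On 9/38 vs 4/31:

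| Test | P |
|---|---|
| One-tailed Fisher | 0.204 |
| Unpooled z | 0.239 |
| Likelihood ratio | 0.248 |
| Welch t | 0.250 |
| Pearson chi-square | 0.255 |
| Student t | 0.261 |
| Boschloo | 0.271 |
| Barnard | 0.286 |
| Fisher mid-P, two-sided | 0.290 |
| Chi-square with Yates correction | 0.407 |

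Moving one count by one and keeping two-tailed Fisher gives 0.526 (8 vs 4), 0.232 (10 vs 4), 0.202 (9 vs 3) and 0.552 (9 vs 5). None of these rounds to 0.22. The list is not exhaustive.

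**Step 5. Size of the difference.** 9/38 − 4/31 = 0.237 − 0.129 = 0.108, or 10.8 percentage points more failures with MLT. The Wilson limits are 0.130 to 0.392 for MLT and 0.051 to 0.289 for SLT. Newcombe's method combines them:

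- lower: 0.108 − √[(0.237 − 0.130)² + (0.289 − 0.129)²] = −0.084
- upper: 0.108 + √[(0.392 − 0.237)² + (0.129 − 0.051)²] = +0.281

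The 95% interval therefore runs from 8 points fewer to 28 points more failures with MLT.

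**The case against.** The strongest reply is that 0.22 can be reached from numbers close to those printed, so the P value may be the correct output of an analysis the document does not describe. There are two such routes.

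- **An ordered outcome.** If patients are ranked as no failure, added drop, and surgery or cyclophotocoagulation, a two-sided asymptotic Mann-Whitney test on all 69 gives P=0.218, or 0.221 with continuity correction. Both round to 0.22.
- **Smaller denominators.** The analysis plan drops responses after certain interventions, and the 24–52-week comparisons imply only 27 and 25 patients. With 9 and 4 failures, two-tailed Fisher rounds to 0.22 for ten pairs of denominators within 27–38 and 25–31, for example 34 and 31 (0.222).

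Both calculations are right, but neither rescues the printed result. The first is not the specified test, and nothing in the document mentions it. The second conflicts with the printed percentages: 9/34 is 26.5%, not 23.7%, and all ten pairs have an MLT denominator of 34 or less, whereas 23.7% requires 38. If either route was taken, the test or the denominator went unreported, and that needs correcting too. What stands is that the origin of 0.22 is unknown, so the source data should be checked before a new number is put in.

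It can also be said that the weight is small, because the conclusion does not change, and that the Results never claim equal failure rates. Both points are fair. They limit how serious the error is and make the added interval optional, but they do not make the printed figure right.

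**Conclusion.** The concern holds. On the document's own percentages, arm sizes and specified test, the P value for total failures is 0.36, not 0.22. The counts 9/38 and 4/31 follow uniquely from the printed figures. The one assumption is that the P value was meant to compare the same 69 patients as the percentages beside it. The log-rank P of 0.31 is a different analysis and does not account for 0.22.

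Neither value is significant at 0.05, so the statement of no significant difference stands. The error is one of reporting, of moderate weight, and it should be fixed. With 13 failures in all and an interval from −8 to +28 points, the comparison does not establish that the two failure rates are similar.

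**What to change.** Check the failure comparison against the source data and confirm the counts, the denominators and the test.

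- If all 69 patients were compared, replace P=0.22 with P=0.36 (two-tailed Fisher's exact test, 9/38 vs 4/31).
- If another test or a smaller patient set was used, name it, give its denominators, and report the specified test on all randomised patients alongside.
- Preferably, print the counts and the risk difference of 10.8 points (Newcombe 95% CI −8 to +28).

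The cost is one number checked and corrected, plus one optional interval. It needs no new data and no change to the design.
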